#### 5.3.3 Statistical significance

For hypothesis tests two-tailed p-values<0.05 are considered statistically significant. Likelihood ratio tests will be used in preference to Wald tests for hypothesis testing.

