# 3. STUDY POPULATION

The study population is all patients recruited into the trial satisfying the main eligibility criteria: aged between 18 and 60 years who have had visual impairment due to CSCR for at least four months (defined as subfoveal presence of SRF on OCT, characteristic appearance of CSCR on FFA and ICGA, and an investigator believes there is sufficient evidence that CSCR has been present for at least 4 months). For specific inclusion/exclusion criteria see **Figure F1**.

Recruitment over time against targets will be presented overall (Figure F2).

The planned sample size for the VICI study is 104 patients. This sample size is sufficient to detect a difference of 5 letters in BCVA between the eplerenone and placebo groups with 90% power and 5% significance (2-tailed), assuming that: the standard deviation is 9 letters; the correlation between baseline and any follow up assessment is 0.5; on average, there will be a minimum of 2 follow up assessments per patient with a correlation between BCVA on follow-up visits of 0.8; up to 15% dropout will occur over the 12 month period.

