- Time to event outcomes will be summarised by the median and IQR in each treatment group, estimated from Kaplan Meier curves. Outcomes will be compared using proportional hazards parametric survival models for interval-censored data. If the assumption of proportional hazards does not hold, other methods will be considered as appropriate. The choice of model used will depend on the outcome event and model assumptions. Treatment comparisons will be presented as hazard ratios (HRs) and 95% CI if a proportional hazards model is used, time ratios (TRs) and 95% CI if an accelerated failure time model is used, or odds ratios (OR) and 95% CI if a discrete time proportional odds model is used. Times will be censored using censoring variables defined below:

Outcome	Censor variable
Time to resolution of SRF	Date of last visit, if SRF did not resolve
Time to disease recurrence	Date of last visit, if SRF did not recur
Time to response (complete or partial)	Date of last visit, if disease did not resolve completely or partially
Time to incidence of CSCR in fellow eye	Date of last visit, if CSCR not present in fellow eye at any point by the end of follow-up

- Continuous longitudinal outcomes will be summarised as means and SDs (or medians and IQRs if distributions are skewed) at each time point. Outcomes will be compared using linear mixed effects methodology where the outcome of interest is collected at baseline, 4 weeks, 3, 6, 9 and 12 months, with the treatment group and study design variables fitted as per section 5.2.1, and patient terms fitted as random effects. Separate parameter estimates will be incorporated into models for 1) the mean baseline response across both treatment groups and 2) at each post-intervention time point for each treatment (i.e. saturated model with time fitted as a categorical variable). If the time x treatment interaction (postintervention) is not statistically significant at the 5% level an overall treatment effect will be reported. If the interaction is statistically significant the changes in treatment effect with time will be described. Different variance/covariance structures will be explored, and the structure that provides the best fit in terms of information criteria such as AIC, BIC and likelihood ratio tests will be used. Treatment comparisons will be presented as adjusted differences in means with 95% CI.

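### SAP section 5.3.3 prefers likelihood ratio tests for all models and names no small-sample reference, so the nominal 5% mixed-model tests run at about 5.3% to 6.5%, depending on the covariance structure

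*SAP*

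**What the plan says.** SAP section 5.3.3 sets the threshold, "For hypothesis tests two-tailed p-values<0.05 are considered statistically significant", and then the type of test: "Likelihood ratio tests will be used in preference to Wald tests for hypothesis testing". The rule is general. It does not mention ML or REML, a chi-square or F reference, or a degrees-of-freedom correction.

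For the longitudinal outcomes, including the primary outcome BCVA, section 5.3.2 says "Outcomes will be compared using linear mixed effects methodology". Time is categorical, with five post-baseline visits, and patient terms are random. The interaction of time and treatment is tested first at 5%. If it is not significant, a single overall effect is reported. The variance structure is to be explored and chosen by fit. Section 5.3.1 intends centre to be a random effect in all models.

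Section 3 gives the size: "The planned sample size for the VICI study is 104 patients", with up to 15% dropout. Section 5.3.8 keeps every patient with at least one observation in the longitudinal models.

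**The concern.** Preferring likelihood ratio tests to Wald tests is sensible for logistic and survival models. For fixed effects in a linear mixed model it has a cost. REML likelihoods of models with different fixed effects cannot be compared, so the test must be run under ML. Its usual chi-square reference takes no account of the degrees of freedom spent on estimating the means and the covariance matrix. At about 100 patients the test then rejects a little too often, even when every model assumption holds. Section 5.3.4, which allows other methods if assumptions fail, therefore does not help.

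Two declared 5% tests are exposed: the overall treatment effect on BCVA, and the interaction test that decides how the primary result is reported. The customary corrections, Kenward-Roger and Satterthwaite, are Wald-type F or t tests, so the written preference points away from them.

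**Working it through.** **Inputs from SAP section 3.** Total 104, difference 5 letters, 90% power, two-sided 5%; "the standard deviation is 9 letters"; "the correlation between baseline and any follow up assessment is 0.5"; two follow-up assessments correlated 0.8; 15% dropout.

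**Sample size reproduced.** The variance factor for a baseline-adjusted mean of two assessments is (1 + 0.8)/2 − 0.5² = 0.65. Per arm, n = 2 × 81 × 0.65 × (1.960 + 1.282)² / 25 = 44.26. The total is 88.5, and 88.5/0.85 = 104.1, which agrees with 104. The two sizes used below are 104 (planned) and 88 (104 × 0.85 = 88.4).

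**Method.** For complete normal data the ML likelihood ratio statistic is a known function of an F statistic, so the true size of the chi-square test can be calculated. Each arm mean is adjusted for an intercept, baseline and visual acuity level. The 5% chi-square cut-offs are 3.841 (1 df) and 9.488 (4 df).

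*Unstructured covariance over five visits*
- Overall effect: statistic n·ln(1 + F/v), with v = n − 8. Reject if F > v(exp(3.841/n) − 1). For n = 88: 80 × 0.04462 = 3.570 on (1, 80) df. For n = 104: 96 × 0.03763 = 3.612 on (1, 96) df.
- Interaction: statistic −n·ln(Wilks' lambda). Reject if F > ((n − 7)/4)(exp(9.488/n) − 1). For n = 88: 81/4 × 0.11384 = 2.305 on (4, 81) df. For n = 104: 97/4 × 0.09552 = 2.316 on (4, 97) df.

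*Patient random intercept*
- Overall effect: as above with v = n − 4. Cut-offs are 84 × 0.04462 = 3.748 on (1, 84) df and 100 × 0.03763 = 3.763 on (1, 100) df.
- Interaction: 4n within-patient contrasts with 4(n − 2) residual df. Reject if F > (n − 2)(exp(9.488/(4n)) − 1). Cut-offs are 86 × 0.02732 = 2.350 on (4, 344) df and 102 × 0.02307 = 2.353 on (4, 408) df.

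| True size of a nominal 5% test | n = 88 | n = 104 |
|---|---|---|
| Unstructured, overall effect | 6.25% | 6.04% |
| Unstructured, interaction | 6.5% | 6.3% |
| Random intercept, overall effect | 5.6% | 5.5% |
| Random intercept, interaction | 5.4% | 5.3% |

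**Simulation checks.** With unstructured covariance and 40,000 runs per size, the interaction test rejected in 6.7% (n = 88) and 6.2% (n = 104), and the overall test in 6.2% and 6.0%. With a random intercept plus a random centre effect and 5,500 runs per size, the overall test rejected in 5.9% and 5.5%, and the interaction test in 5.5% and 5.4%. That second set assumes 20 centres and a centre variance of 4, neither of which is in the SAP, and applies 15% dropout at n = 104. In the complete-data cases an F or t reference with matching df restores 5.0%.

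**The alternative that the SAP rejects.** These are uncorrected Wald tests against chi-square, unstructured covariance, 20,000 runs per size:

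| | Likelihood ratio | ML Wald | REML Wald |
|---|---|---|---|
| Interaction, n = 88 | 6.6% | 7.8% | 6.8% |
| Overall, n = 88 | 6.6% | 7.6% | 6.9% |
| Interaction, n = 104 | 6.2% | 7.3% | 6.4% |
| Overall, n = 104 | 5.8% | 6.7% | 6.1% |

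With a random intercept, a REML Wald test of the overall effect against the normal distribution has size 5.3% at both sample sizes. That is slightly nearer 5% than the likelihood ratio test but still above it.

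**The case against.** The case for leaving the text alone is fair on several counts. Likelihood ratio inference in mixed models is common practice. With an unstructured covariance the sentence in section 5.3.3 chooses the less liberal of the two uncorrected tests, so the preference is not itself the cause of the excess. Section 5.3.8 retains every patient with at least one observation, so the number contributing is nearer 104 than 88, and the excess is smaller there. All of this stands. It does not supply a reference distribution, and the excess is still present at 104.

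A reader might go further in four ways that the SAP does not support:

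- **That section 5.3.3 forces a chi-square ML test.** It states a preference and names neither ML nor chi-square. A corrected likelihood ratio test would comply. The uncorrected test is the natural default, no more.
- **That the tests run at 6.0% to 6.5%, or give 25% to 30% more false positives.** Those figures (6.25/5 = 1.25; 6.5/5 = 1.30) belong to the unstructured case, and the relative ones to n = 88. A random intercept is equally open under section 5.3.2.
- **That the confidence intervals are too narrow.** The sentence concerns hypothesis tests only, and nothing says how intervals are obtained.
- **That the 12-month continuous outcomes lose an exact t-test.** Section 5.3.1 intends a random centre effect there too, so these are mixed models as planned. Above 5% missing data, section 5.3.8 also considers multiple imputation, where pooled inference is normally t-based.

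**Conclusion.** The point holds as a minor one. Without a small-sample reference, the usual chi-square ML tests are liberal under both structures examined: about 5.3% to 5.6% with a patient random intercept, and about 6.0% to 6.5% with an unstructured covariance.

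The exact figures assume complete normal data, conditioning on baseline and visual acuity level, and no centre effect. The simulation with random centres gave 5.4% to 5.9%. The extra error from choosing the covariance structure on the data, or from testing the interaction first, was not modelled.

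The practical reach is short. For the overall effect, an exact p-value of 0.05 corresponds to a chi-square p-value of about 0.039 with unstructured covariance at n = 88 (F = 3.960 on 80 df; 88 × ln(1 + 3.960/80) = 4.252). With a random intercept at n = 104 it corresponds to about 0.045 (F = 3.936 on 100 df; 104 × ln(1 + 3.936/100) = 4.015). Only a result between that value and 0.05 would change sides.

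**What to change.** Amend section 5.3.3 so that the likelihood ratio preference applies to the logistic and survival models only. For the linear mixed models, state that they are fitted by REML, with Kenward-Roger (or Satterthwaite) F or t tests and matching confidence intervals. This covers BCVA, low-luminance BCVA and CSRT, and also the 12-month continuous outcomes wherever centre is a random effect. Use the ordinary t-test only where no random effect is fitted, so that the planned centre adjustment is not dropped by accident. Likelihood ratio comparisons of covariance structures can stay, since under REML they are valid when the fixed effects are the same.

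The cost is a sentence or two in the SAP and a software option. The downside is slightly larger p-values: for the overall effect, a chi-square p-value of exactly 0.05 becomes about 0.055 to 0.056 with a random intercept and about 0.060 to 0.062 with an unstructured covariance.

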#### 5.3.4 Model assumptions

For all methods outlined underlying assumptions will be checked using standard methods, e.g. residual plots, tests for proportional hazards, etc. If assumptions are not valid then alternative methods of analysis will be sought.

#### 5.3.5 Subgroup analyses

There are no planned subgroup analyses defined in the study protocol.

#### 5.3.6 Exploratory analyses

An exploratory analysis to assess the effect of adherence and treatment on the primary outcome, BCVA will be performed.

Four indicators will be generated for each post-randomisation time point at which the primary outcome was assessed:

- 1. Patient on treatment and adhered
- 2. Patient on treatment and did not adhere
- 3. Patient not on treatment due to disease resolution
- 4. Patient not on treatment for any other reason

The proportion of time spent in each of the respective categories during the previous period will be calculated (e.g. 25% of period on treatment and adhered and 75% not on treatment due to disease resolution, would be coded as 0.25 for indicator 1 and 0.75 for indicator 3) as indicators of adherence. If possible, interactions between treatment group and each of these indicators will be added to the model and indicator status-specific effects will be estimated for each treatment group. If preliminary analyses suggest that some parameters cannot be estimated reliably a simpler model will be sought (e.g. fitting indicators of treatment and adherence, but not proportion of time on treatment etc.).

Additional exploratory analyses of the overall trial cohort will assess the association between:

- (a) Age of the patient at randomisation and visual acuity;
- (b) Presence of granular/confluent hypoautofluorescence in the macula at

randomisation and final visual acuity

The analyses will be adjusted for treatment group.

#### 5.3.7 Sensitivity analyses

There are no planned sensitivity analyses defined in the study protocol. In the exploratory analysis assessing adherence, when calculating adherence, the assumption will be made that if a bottle is confirmed as lost, there were no pills remaining in the bottle. A sensitivity analysis on this exploratory analysis will be carried out by imputing the number of pills remaining in bottles that are confirmed as lost.

A sensitivity analysis for binary outcomes measured at 12 months will be performed if there is differential drop-out between treatment groups. Note this analysis was not pre-specified in the protocol. This will be performed by: (a) assuming missing values = no, and (b) assuming missing values = yes.

An initial review of baseline data found imbalances between treatment groups in some prognostic factors. For analyses of outcomes which have a baseline measure, this imbalance will be taken into account. For other outcomes (e.g. time to event outcomes) no adjustment for baseline was planned; for these outcomes a post-hoc analysis will be performed adjusting for factor(s) imbalanced at baseline.

#### 5.3.8 Missing data

In all tables missing data will be indicated by footnotes. If the amount of missing data differs substantially between treatment groups potential reasons will be explored.

#### Missing predictors:

There will be no missing data for any of the randomisation factors (by design). All other potential predictors are baseline measurements of continuous longitudinal outcomes, and due to the modelling approach described previously the handling of missing values for such data is considered in the context of missing longitudinal data (see below).

Missing outcomes measured at one time point:

• If the proportion of missing data is less than 5% then complete case analysis will be performed (i.e. excluding cases with missing data).

 If the proportion of missing data is above 5% multiple imputation methods will be considered. A general imputation model that uses an iterative procedure to generate imputed values will be used to generate multiple complete data sets (e.g. using Stata's mi impute). The model of interest will be the fitted to each of the complete data sets and effect estimates combined using Rubin's rules. If appropriate, methods such as predictive mean matching will be used in order to ensure that imputed values lie within specific ranges.

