#### 3. Change in sub-retinal fluid thickness

Sub-retinal fluid thickness is measured in the study eye by OCT. Measurements at baseline and 12 months will be used to derive this outcome. Change in sub-retinal fluid thickness will be described; sub-retinal fluid thickness at 12 months will be compared between groups, adjusting for baseline.

New variable	Rules	
Sub-retinal fluid thickness (study eye)	If 'Is maximum SRF at fovea?' (SE_OCT_IsMaxSRFAtFovea) = YES; then = 'Height of SRF at fovea' (SE_OCT_HeightSRFAtFovea) Else if 'Is maximum SRF at fovea?' = NO; then = 'If no, measure height of maximum SRF' (SE_OCT_HeightMaxSRF) Else = Missing	
Change in sub-retinal fluid thickness	
 
= (sub-retinal fluid thickness at 12 months – sub-retinal fluid thickness at baseline)
 
	

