#### 5.3.2 Analysis models

All outcomes listed in the study protocol will be presented as per the template tables **Table T14** to **T18**. General methods of presentation and assessing treatment effects are outlined below. For all treatment comparisons, the placebo with usual care group will be the reference group. Details specific to each outcome are described as appropriate.

Each outcome will be considered under a certain data type, as outlined in the table below:

Date type	Outcomes
Binary	Proportion of patients with macular atrophy of the RPE Proportion of patients with reduced choroidal permeability
Continuous	Sub-retinal fluid thickness Area of macular RPE hypoautofluorescence Patient-reported visual function (VFQ-25) Choroidal thickness
Time to event	Time to resolution of SRF Time to disease recurrence Time to complete or partial resolution Incidence of CSCR in fellow eye
Longitudinal	BCVA (primary) Low luminance BCVA CSRT
Descriptive	Systemic and ocular adverse events Classification of all study eyes as complete, partial or no resolution of SRF Classification of all study eyes by each FFA phenotype

Each type of data will be summarised and compared between the groups according to the following:

- **Binary outcomes** will be presented as numbers and percentages of patients in each treatment group experiencing the outcome at 12 months. Outcomes will be compared between treatment groups using logistic regression, with treatment comparison estimates presented as adjusted odds ratios (OR) and 95% confidence intervals (95% CI). Formal statistical comparisons of treatment effects will only be performed if more than ten patients in total experience the outcome (with at least one event in each treatment group).
- Continuous outcomes measured 12 months only (with or without baseline values) will be summarised by the mean change and SD in each treatment group if distributions are approximately normal, or the median and IQR if data are non-normal. In patient-reported visual function, mean and SD at 12 months will be summarised and models adjusted for baseline. Outcomes will be compared using linear regression. For untransformed data treatment comparisons will be presented as adjusted differences in means with 95% CI, and for logarithmically transformed data as adjusted geometric mean ratios (GMRs) with 95% CI.

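### The missing-predictor rule wrongly treats every baseline covariate as belonging to a longitudinal outcome, so missing baselines in four linear regressions and in the post-hoc time-to-event models have no valid stated method

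*SAP*

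**What the plan says.** Section 5.3.8, under missing predictors, first notes that the randomisation factors cannot be missing. It continues: "All other potential predictors are baseline measurements of continuous longitudinal outcomes". From this it concludes that "the handling of missing values for such data is considered in the context of missing longitudinal data (see below". The longitudinal paragraph it points to deals with baselines by modelling them jointly with the follow-up values.

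The outcome table in section 5.3.2 lists three longitudinal outcomes: "BCVA (primary) Low luminance BCVA CSRT". A separate continuous class holds four: "Sub-retinal fluid thickness Area of macular RPE hypoautofluorescence Patient-reported visual function (VFQ-25) Choroidal thickness". That class is defined as outcomes "measured 12 months only (with or without baseline values"), and for it "Outcomes will be compared using linear regression".

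Baseline enters these four regressions as follows:

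- SRF thickness (section 4.2, item 3): "sub-retinal fluid thickness at 12 months will be compared between groups, adjusting for baseline".
- Hypoautofluorescence area (section 4.2, item 6): the 12-month area is analysed with adjustment for baseline.
- VFQ-25 (section 5.3.2): "In patient-reported visual function, mean and SD at 12 months will be summarised and models adjusted for baseline".
- Choroidal thickness: no outcome-specific sentence, but section 5.3.1 makes baseline a covariate for any continuous outcome also measured before treatment, and Table T17 has a baseline row for it.

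Section 5.3.7 adds post-hoc time-to-event analyses adjusted for baseline factors found to be imbalanced. It does not name those factors.

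**The concern.** The missing-predictor rule works only if every non-randomisation covariate is the baseline of an outcome fitted by the joint longitudinal model. If some are not, the rule points the analyst to a model that is not being fitted, and nothing else in section 5.3.8 says what to do with a missing baseline.

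An ordinary linear regression with an incomplete covariate omits the incomplete rows by default. A participant with a 12-month scan or questionnaire but no baseline value would then drop out of that comparison, although the outcome was observed. The choice would also be made at analysis, in a plan whose version 2.0 was already amended after an initial look at the data. A written rule is worth having for that reason, even if few values turn out to be missing.

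**Working it through.** **Step 1: does the premise hold?** Setting section 5.3.2 against section 5.3.8:

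| Outcome | Class in 5.3.2 | Baseline covariate | Covered by the joint model? |
|---|---|---|---|
| BCVA | Longitudinal | Yes | Yes |
| Low luminance BCVA | Longitudinal | Yes | Yes |
| CSRT | Longitudinal | Yes | Yes |
| SRF thickness | Continuous, linear regression | Yes (4.2) | No |
| Hypoautofluorescence area | Continuous, linear regression | Yes (4.2) | No |
| VFQ-25 | Continuous, linear regression | Yes (5.3.2) | No |
| Choroidal thickness | Continuous, linear regression | Yes (5.3.1 with Table T17) | No |

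Of seven continuous outcomes with a baseline covariate, three fit the premise and four do not. The imbalanced factors in section 5.3.7 are a further set that need not be baselines of longitudinal outcomes.

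**Step 2: does another rule reach these covariates?** The remaining paragraph of section 5.3.8 is headed as applying to missing outcomes at one time point. It sets complete-case analysis below 5% missing and says that multiple imputation will be considered above 5%. It does not say whether a missing baseline counts towards the 5%, or whether the baseline is in the imputation model.

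**Step 3: the plan's own figure.** The rule carries no number, so the only figure to reproduce is the sample size in section 3. With 2 follow-ups, correlation 0.8 between them and 0.5 with baseline, the variance factor is f = (1 + 0.8)/2 − 0.5² = 0.65. Per arm, n = 2 × 9² × 0.65 × (1.960 + 1.282)² / 5² = 44.26. Then 2 × 44.26 / 0.85 = 104.1, which agrees with the stated 104. This point does not affect it. After 15% dropout, 104 × 0.85 = 88.4, so about 88 participants have a 12-month value.

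**Step 4: cost if nothing is imputed.** The SAP gives no baseline missing rate, so m is an assumption. If a fraction m of participants with an outcome is lost:

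- participants lost = 88 × m
- standard error ratio = 1/√(1 − m)
- power of a comparison that would otherwise have 90% = Φ[(1.960 + 1.282) × √(1 − m) − 1.960]

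| Assumed m | Lost of 88 | Standard error rises by | 90% power becomes |
|---|---|---|---|
| 1% | 0.9 | 0.5% | 89.7% |
| 5% | 4.4 | 2.6% | 88.5% |
| 10% | 8.8 | 5.4% | 86.8% |

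The power column is only a yardstick, because the SAP states no power for any secondary outcome. The fix would recover most of this loss but not all, since a participant without a baseline contributes less information than one with it.

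**The case against.** A reader might infer that the SAP instructs the analyst to drop everyone without a baseline value. It does not. Deletion is what software does when nothing is specified, and it matches the complete-case branch below 5% if that branch is borrowed for covariates. Above 5%, imputation is to be considered with a general iterative model that produces complete data sets, and such a model could fill in baselines too. That part of the objection stands: the fault is an unspecified step resting on a false premise, not a deletion rule.

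A reader might also see a breach of the modified intention-to-treat population in section 3.5. That section defines who belongs to the population. It does not promise that every model uses every member, and section 5.3.8 openly accepts complete-case analysis at low missingness. Nor is bias shown: these baselines precede treatment, so the cost is mainly precision.

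The number affected may be small. Eligibility requires subfoveal fluid on OCT, so nearly everyone should have a pre-randomisation OCT, the source of both SRF and choroidal thickness. The 15% in section 3 is dropout during follow-up and says nothing about baseline. The lower rows of assumed missingness are therefore quite plausible, although ungradable images and missing autofluorescence or VFQ-25 baselines remain possible.

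Finally, baseline plus 12 months could be read as data at multiple time points, which would bring the four outcomes under the joint model. Section 5.3.2 closes that route, because it assigns them to linear regression and reserves the mixed model for outcomes collected at baseline, 4 weeks, 3, 6, 9 and 12 months.

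**Conclusion.** The statement in section 5.3.8 is wrong within the SAP itself. Missing baselines for the four linear-regression outcomes, and missing values of any baseline factors added in the section 5.3.7 post-hoc models, have no valid stated method. Without imputation, participants whose outcome was observed are lost from these secondary analyses.

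The point is minor. Its size depends on a missing rate that the document does not give; across the assumed range of 1% to 10%, about 1 to 9 of 88 participants would be lost per outcome. The standard error figures assume that the lost participants are otherwise like the rest. The primary outcome and the planned sample size are not touched. The amendment that moved choroidal thickness from longitudinal to continuous may explain the mismatch for that outcome, but not for the other three.

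**What to change.** Correct the sentence in section 5.3.8 so that it limits the longitudinal rule to BCVA, low luminance BCVA and CSRT. Then add a rule along these lines:

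- For SRF thickness, hypoautofluorescence area, VFQ-25 and choroidal thickness, a missing baseline covariate is replaced by the mean of all observed baselines pooled over both arms, on the scale used in the model. Alternatively, baseline and 12 months are fitted jointly with a common baseline mean. The SAP should name one of the two.
- Where multiple imputation is used for the outcome, the baseline is included in the imputation model.
- The same handling applies to baseline covariates in the post-hoc time-to-event models of section 5.3.7.

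Every participant with a 12-month value then stays in the four regressions. The cost is a few sentences in the SAP and trivial programming, with no new data and no change to the primary analysis.
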